#### 5.2 Exclusion criteria

E1. Breastfeeding women,

- E2. Treatment with systemic glucocorticoids greater than 10 mg prednisone or the equivalent per day within 4 weeks prior to screening,
- E3. Any treatment with glucosamine or chondroitin sulfate in the previous 3 months,
- E4. Any glucagon-like peptide 1 analogue hormones,
- E5. Anticoagulant treatment (current or within the last 10 days),
- E6. Treatment of the target knee with any IA injection (steroids, hyaluronic acid derivatives, PRP ....) within 3 months,
- E7. Knee surgery (of the target knee) performed within the previous 12 months or planned within the next 6 months,
- E8. Any partial knee replacement of the target knee,
- E9. Any known active infections or increased predisposition for the development of infections E10. Clinical signs and symptoms of active joint crystal disease, or any inflammatory joint disease,
- E11. Diabetes type I or II,
- E12. Congestive Heart Failure stage III or IV of NYHA classification,
- E13. Inflammatory bowel disease,
- E14. Any other chronic condition that has not been well controlled for a minimum of 3 months.
- E15. History of malignancy of any organ system (other than localized basal cell carcinoma of the skin or in-situ cervical cancer) within the last 5 years,
- E16. Any condition, including laboratory findings, that in the opinion of the investigator constitutes a risk or contraindication for participation in the study or that could interfere with the study objectives, conduct or evaluation, (for example, any abnormal reaction to previous IA injection),
- E17. Hypersensitivity to the active substance liraglutide or to any of the excipients: Disodium phosphate dihydrate, Propylene glycol, Phenol,
- E18. Participation in an interventional clinical research trial within 12 weeks prior.

#### 5.3 Screen failures

Screen failures are defined as participants who consent to participate in the clinical study but are not subsequently randomly assigned to the IMP. A minimal set of screen failure information is required to ensure transparent reporting of screen failure participants to meet the Consolidated Standards of Reporting Trials (CONSORT) publishing requirements and to respond to queries from regulatory authorities. Minimal information includes demography, screen failure reasons, eligibility criteria, and any SAEs.

Participant numbers assigned to subjects who fail screening should not be reused. If a participant fails screening but is later successfully rescreened (Individuals who are defined as screen failures may be rescreened once), the data for the participant will be entered as if these were 2 separate participants.

Therefore, the data should be entered as follows:

• The screen failure data should be entered as a screen failure participant.

 Rescreened participant should be assigned a new participant number and treated as a standalone participant.

## **6 STUDY INTERVENTION**

## 6.1 Study intervention administered

A complete description of the IMP and its proper handling will be provided in the Pharmacy manual available to the clinical site.

#### 6.1.1 Liraglutide

Liraglutide will be provided at 6 mg per mL in a clear and colourless or almost colourless, isotonic solution, pH=8.15. Solution also contains disodium phosphate dihydrate, propylene glycol, phenol and water.

#### 6.1.2 Placebo

NaCl 0.9% sterile solution will be used as placebo.

NaCl 0.9% solution is commonly used in biological research.

## 6.2 Preparation / Handling / Storage /Accountability

A complete description of the Investigational Medicinal Product (IMP) preparation, handling, storage and accountability will be provided in the Pharmacy manual available to the clinical site.

The product should be stored in a refrigerator (2°C–8°C), away from the freezer compartment. It should not be freeze. Sites are requested to maintain a temperature log according to their SOP to ensure storage temperature remains within acceptable limits.

The pharmacist who will be responsible for IMP preparation in an unblinded condition will be responsible for IMP accountability, reconciliation, and record maintenance (i.e., receipt, reconciliation, and final disposition records).

The used pen will be kept by the Pharmacist in a secure location up to the full documented reconciliations performed with the Sponsor at the end of the study. The Pharmacist should wait for the written approval form from the Sponsor before proceeding to their destruction. Any annotation on the box containing the pen should be considered as source documents until the time of pen destruction.

## 6.2.1 IMP preparation, administration and handlings

Dilution will be made according to the dose to get a total volume to be injected intraarticularly. Details are provided in the Pharmacy manual.

#### 6.2.2 IA injection

The IMP will be administered by IA injection. A complete and detailed description can be found in the Investigator manual. It is recommended, but not mandatory, to do the IA injection with ultrasound guide.

Use of local anesthetic agent (lidocaine or other) or X-ray contrast agent are not allowed to avoid any interference with the IMP.

The skin is cleansed and sterilized.

The sterile needle 0.8 x 50mm (type Becton Dickinson Microlance™ 3 Aiguilles 21G 2RB green is inserted in the knee IA joint space.

The injection itself (with a second syringe prepared with IMP, see Investigator manual) is possibly preceded by an aspiration phase of the synovial fluid, if any, to

- i) free the knee from the tension linked to the excess volume of synovial fluid in the knee,
- ii) make laboratory assessment of the synovial fluid as per standard practice.

## 6.3 Measures to minimize bias: randomization and blinding

All consented participants will be given a unique screening number that will be used to identify the participant for all procedures. Screening numbers must not be re-used for different participants. Participants can be rescreened once.

#### Randomization

Randomization will be performed using a pre-established randomization list. This list will be generated by a statistician for the IMPs (4P-004 or placebo) based on study design (sequential randomization according to the dose escalation and sentinel patients).

The randomization will be requested by the site at visit 2 (on D1) after eligibility confirmation. Participants will be assigned their treatment according to the randomization schedule in the order in which they are randomized into the study.

Product code lists (4P-004 or placebo) will be generated and managed by the unblinded responsible person delegated by the sponsor.

The unblinded responsible person will communicate the result of the randomization (arm 4P-004 or placebo) and the associated product code to the pharmacy of PI site.

Except for the unblinded pharmacist who will prepare the IMP, the Investigator and the whole study team will remain blinded for the study IMP.

Complete instructions will be provided to the site in the randomization and code break procedure. In case a participant needs to be replaced, the replacement participant should receive the same treatment that the participant being replaced would have received. The unblinded responsible person will attribute the replacement code to the next patient.

#### **Unblinding**

In case of an emergency, the Investigator has the sole responsibility for determining if the unblinding of a participant's intervention assignment is warranted (e.g., in case of an AE, the code must only be broken in circumstances when the knowledge of the IMP is required for treating the participant). Participant safety must always be the first consideration when making such a decision. If the Investigator decides that the unblinding is warranted, the Investigator should make every effort to contact the Sponsor prior to unblinding a participant's intervention assignment, unless this could delay emergency treatment of the participant. Code breaking can be performed at any time by using the sealed envelope handled by the Investigator. If a participant's intervention assignment is unblinded, the Sponsor must be notified immediately and maximum 24 hours after breaking the blind (details are given in the code break procedure). The date, time of the day, and reason that the blind

was broken must be recorded in the source documentation and electronic case report form (eCRF), as applicable. If the code is broken by the Investigator, the participant must be withdrawn from the study treatment.

## Methods of blinding

This is a double-blind study but the Pharmacist who will prepare the IMP material to be injected will not be blinded. Only the Pharmacist who has not any contact with the participant will be unblinded. The DSMB will have access to unblinded data if deemed necessary by the DSMB. No unblinding information will be shared by the DSMB with the study team excepted the unblinded responsible person who will provide tables for the DSMB open/closed sessions. Details about the distribution of unblinding data to the DSMB while protecting the blind are described in the DSMB charter.

## 6.4 Changes in IMP cohort dosing

## 6.5 Concomitant therapy

Any medication (including over-the-counter or prescription medicines, vitamins, and/or herbal supplements) that the participant is receiving at the time of randomization or receives during the study must be recorded along with:

- Reason for use,
- Dates of administration including start and end dates,
- Dosage information including dose and frequency.

Oral analgesics (paracetamol, non-Steroidal anti-inflammatory drug [NSAID], tramadol, opioids) or topical NSAID if needed are allowed during the study, all treatments taken for pain relief will be recorded in the eCRF (via participant's diary).

Other treatments not listed in exclusion criteria initiated before the study start can be pursued during the whole study and will be recorded in the CRF.

# 7 DISCONTINUATION OF STUDY INTERVENTION AND PARTICIPANT WITHDRAWAL

#### 7.1 Discontinuation of study intervention

NA

#### 7.2 Participant discontinuation / Withdrawal from the study

A participant may withdraw from the study at any time at his/her own request or may withdraw at any time at the discretion of the Investigator for safety, behavioral, compliance, or administrative reasons. In these situations, if possible, the D8 visit should be performed if discontinuation is before.

Clarification should be made with the participant if

• he/she does not want to come back to next scheduled or

he/she does not want anymore his/her data to be analyzed for the purpose of the study

The Investigator should make every effort to perform the EoS Visit.

All study withdrawals should be recorded by the Investigator in the appropriate screens of the eCRF and in the participant's medical records. In the medical record, at least the date of the withdrawal and the reason should be documented.

In addition, a participant may withdraw his/her consent to stop participating in the study. If the participant withdraws consent for disclosure of future information, the Sponsor may retain and continue to use any data collected before such a withdrawal of consent. If a participant withdraws from the study, he/she may request destruction of any samples taken and not tested (e.g., archival samples for future use), and the Investigator must document this in the site study records. The site should document any case of withdrawal of consent.

Should participant withdraw from the study between D1 and D8, or at any later time, participants replacement will be evaluated on a case-by-case basis.

## 7.3 Lost to follow up

A participant will be considered lost to follow-up if he or she repeatedly fails to return for scheduled visits and is unable to be contacted by the study site.

The following actions must be taken if a participant fails to return to the clinic for a required study visit:

- The site must attempt to contact the participant and reschedule the missed visit as soon as possible and counsel the participant on the importance of maintaining the assigned visit schedule and ascertain whether the participant wishes to and/or should continue in the study.
- Before a participant is deemed lost to follow up, the Investigator or designee must make every effort to regain contact with the participant (where possible, several telephone calls and, if necessary, a certified letter to the participant's last known mailing address or local equivalent methods). These contact attempts should be documented in the participant's medical record.
- Should the participant continue to be unreachable, he/she will be considered to have withdrawn from the study.

The Statistical Analysis Plan (SAP) will specify how these participants lost to follow-up for their primary endpoints will be considered.

## **8 STUDY ASSESSMENTS AND PROCEDURES**

Study procedures and their timing are summarized in the Study Flowcharts (section 1.2).

Adherence to the study design requirements, including those specified in the Study Flowchart is essential and required for study conduct.

All Screening evaluations must be completed and reviewed to confirm that potential participants meet all eligibility criteria. The Investigator will maintain a screening log to record details of all participants screened and to confirm eligibility or record reasons for screening failure, as applicable.

Procedures conducted as part of the participant's routine clinical management and obtained before signing of the informed consent form (ICF) may be utilized for screening purposes provided the procedures met the protocol-specified criteria and were performed within the time frame defined in the Study Flowchart and/or in inclusion or exclusion criteria (see sections 1.2, 5.1, 5.2).

The maximum amount of blood collected from each participant over the duration of the study, including any extra assessments that may be required, will not exceed 100 mL(the exact assessment specific volumes are described in section 11.2) within approximately 14 days. Repeated or unscheduled samples may be taken for safety reasons or for technical issues with the samples.

## 8.1 Safety assessments

Planned time points for all safety assessments are provided in the Study Flowchart.

#### 8.1.1 Physical examination

A physical examination will be conducted at screening, D1, D2 and D8 visits. A symptom-based physical examination will include organ systems, which are deemed, at the discretion of the Investigator, necessary to be evaluated.

Height (at screening only) and weight will also be measured at screening, D1 and D8 and recorded (Body mass index will be calculated automatically).

## 8.1.2 Vital signs

Vital signs will be measured at screening and D1, D2 and D8 as outlined in the Study flowcharts (see Section 1.2). They will be measured in a sitting position after 5 minutes of rest and will include systolic and diastolic blood pressure, and pulse. Blood pressure and pulse measurements will be assessed with a completely automated device. Manual techniques will be used only if an automated device is not available.

#### 8.1.3 Electrocardiograms

Three 12-lead ECG will be obtained at screening and D1 as outlined in the Study flowcharts (see section 1.2).

Electrocardiogram parameters will be based upon the automatic reading of the device. These ECG parameters and morphology need to be reviewed by the Investigator. If the device does not provide automatic reading, then the ECG parameters will need to be determined and interpreted by the Investigator.

#### 8.1.4 Clinical safety laboratory assessment

See section 11.2 for the list of clinical safety laboratory tests to be performed and section 1.2 (Study flowcharts) for the timing and frequency.

• The Investigator must review the laboratory report, document this review, and record any clinically significant changes occurring during the study in the AE section of the eCRF. The laboratory reports must be filed with the source documents. Clinically significant abnormal laboratory findings are those which are not associated with the underlying disease, unless judged by the Investigator to be more severe than expected for the participant's condition.

- All laboratory tests with values considered clinically significantly abnormal during participation in the study or within 4 weeks after the last dose of IMP should be repeated until the values return to normal or baseline or are no longer considered clinically significant by the Investigator or Medical Monitor.
  - ✓ If such values do not return to normal/baseline within a period of time judged reasonable by the Investigator, the etiology should be identified, and the Sponsor notified.
  - ✓ All protocol-required laboratory assessments, as defined in section 11.2, must be conducted in accordance with the Laboratory manual and the Study flowcharts (see section 1.2).
- If laboratory values from non-protocol specified laboratory assessments performed at the institution's local laboratory require a change in participant management or are considered clinically significant by the Investigator (e.g., SAE, AE, or dose modification), then the results must be recorded in the eCRF.

#### 8.1.5 Local safety

The evaluation of IA injection site reaction following IMP administration will be performed by the Investigator or designees as outlined in section 1.2.2. Findings at the site of injection such as, but not limited to tenderness, erythema, and swelling, will be recorded in the eCRF in 3 different grades (mild/moderate/severe).

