## 1.2.2 Visit 2 (randomization): D1-D2 study flowchart (24h hospitalization)

D1 / D2	T0 - 4h*	ТО	1h	2h	3h	4h	5h	6h	8h	10h	12h	16h	24h
Urine Pregnancy Test	Х												
SARS-CoV-2 Rapid Antigen Test	(x)												
Definitive inclusion	X												
Randomization**	X												
Physical Exam	X												Х
Bodyweight	X												
Veinous line	X	Χ	Χ	Х	Χ	Χ	Χ	Χ	Χ	Х	Χ	Χ	Х
IMP IA injection		Χ											
Vital signs	X		Χ	Х		Χ			Χ		Χ		Х
ECG	X										x***		
AEs / SAEs / AESI	X	Χ	Χ	Χ	Х	Х	Х	Х	Χ	Х	Х	Х	Х
Target knee pain	X		Χ	Х	X	X	Χ	Χ					Х
Local reaction			Χ	Х	X	X	Χ						Х
Glycemia	X			Χ		Χ			Х		Χ	Х	
Blood glucose meter	Х		Χ					Χ		Х			Х
Blood PK sample	X			Χ		Χ			Χ		Х	Х	X
Blood sample	Х								Χ				Х
Urine Sample	Х								Χ				Х

[figure not shown]
\*For practical reasons, all procedures planned before T0 (time of administration) can be done within 4 hours before T0.

AEs / SAEs / AESI reporting is continuous during the hospitalization

\*\*Randomization will be done before T0once results of the SARS-CoV-2 test (if required according to standard practice on site) and urine pregnancy test (if necessary) are available. All assessments after T0 must be carried out  $\pm$  10 minutes compared to the theoretical time. \*\*\* A time window of  $\pm$  2 hours for the ECG planned at T0 +12 is allowed

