## **5 STUDY POPULATION**

#### 5.1 Inclusion criteria

- I1. Participants who have the capacity to give informed consent and who are willing to comply with all study related procedures and assessments (consent via legally authorized representative will not be accepted),
- 12. Ambulatory participants, agreeing a 24-hour hospitalization,
- I3. Participants between 18 and 80 years of age,
- I4. Female participant of childbearing potential (WOCBP), must use contraceptive consistent with local regulations regarding the methods of contraception for those participating in clinical studies (see section 11.4) for at least 5 days following IMP injection, and must have a negative urine pregnancy test done within 24h before randomization,
- I5. Male participants (whose partners are of childbearing potential) must consent to use methods of contraception consistent with local regulations regarding the methods of contraception for those participating in clinical studies (see section 11.4), for at least 90 days following IMP injection,
- I6. Participants with knee osteoarthritis, KL 2-4 of their target knee (defined at screening as the knee with greater pain based on the participant's evaluation and the investigator's clinical judgment),
- 17. X-ray of the target knee within 6 months (if not, to be performed before randomization),
- I8. ECG within normal range,
- I9. WBC (white blood cell count)  $> 3500/\mu L$ ,
- I10. Hemoglobin > 12 g/dL,
- I11. Platelets  $> 100,000/ \mu L$ ,
- I12. Creatinine clearance (CrCl) > 60 mL/min,
- I13. Glycemia within normal range,
- I14. AST, ALT < 1.5 upper limit of normal (ULN),
- I15. Amylasemia < 1ULN,
- I16. Negative tests for COVID-19 (if required by the standard practice on site), HIV, HbsAg and hepatitis C Ab (Determination of HIV and hepatitis status can be based on participant-reported medical history, available medical records, and the most recently available laboratory results for the participant [tests performed within the previous 12 months]).

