#### 8.5.2 Inclusion visit, D1, full day hospitalization

During this visit (24 hours hospitalization), the Investigator will:

- review inclusion / exclusion criteria, concomitant medication (from screening),
- do physical exams, ECGs, measure vital signs as per D1-D2 Study Flowchart (section 1.2.2),
- record any AE since screening,
- put a veinous line,
- remind the participant to fill in the NRS (before any study intervention on D1) for assessing target knee pain in the previous 2 days and during the hospitalization as outlined in section 1.2.2.
- randomize the participant (performed by the pharmacist)
- take blood / urine samples for glycemia, PK and OA-related biomarkers samples as per D1-D2 Study Flowchart (section 1.2.2),
- do the IA injection (modalities given in section 6.2.2 and in the Investigator manual) of the IMP extemporaneously prepared in a vial by the pharmacist (procedure for preparation is detailed in the Pharmacy manual).
- record AEs as per D1-D2 Study Flowchart (section 1.2.2),
- monitor the participant during the coming 24 hours:
  - o on local reaction as per D1-D2 Study Flowchart (section 1.2.2)
  - o on blood sugar level (veinous / capillary measures):
    - after IMP injection, glycemia will be systematically monitored (capillary measures via glucose meter and/or veinous measures) as per D1-D2 Study Flowchart (section 1.2.2),
    - when planned measurement indicates glycemia is ≤ 70 mg/dL without clinical symptom repeat the test each 30 min up to obtaining threshold value >70 mg/dL,
    - at any time if occurrence of one or more symptoms of hypoglycemia (common presenting symptoms include nausea, confusion, tremor, sweating, palpitations, or hunger), sugar will be given to the participant and a blood glycemia test should be immediately performed and closely monitored.

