### 9.4 Derived and Computed Variables

For any variable, the baseline value is defined as the last observation before IMP injection.

The time will be split into 3 periods (epochs):

- before treatment (screening)
- during treatment (from IMP injection to 7 days after IMP injection date)

after treatment

The following PK parameters will be calculated from measured plasma concentrations for each participant:

- Maximum observed concentration (Cmax)
- Time of maximum observed concentration (Tmax)
- Area under the curve (AUC0-t)
- Terminal Half-life (T1/2)

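### No graded look at the target knee for tenderness, erythema or swelling is scheduled before injection, so signs already present can be recorded as injection-site reactions

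*Protocol*

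**What the plan says.** **Schedule.** Protocol 8.1.5 says "The evaluation of IA injection site reaction following IMP administration will be performed by the Investigator or designees as outlined in section 1.2.2". On what is graded, it says "Findings at the site of injection such as, but not limited to tenderness, erythema, and swelling, will be recorded in the eCRF in 3 different"; the scale has three levels, mild, moderate and severe. No condition that a finding be new or worse is attached. In the 1.2.2 flowchart the row "Local reaction" is marked at 1, 2, 3, 4, 5 and 24 hours; the T0-4h and T0 cells are empty. The whole-study flowchart in 1.2.1 marks the row on D1 and D2 only, with nothing at screening. Section 8.5.2 lists it under the monitoring that follows injection: "on local reaction as per D1-D2 Study Flowchart (section 1.2.2").

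**Nearest substitute.** A physical examination is scheduled at screening and at T0-4h, but Protocol 8.1.1 leaves its content open: "A symptom-based physical examination will include organ systems, which are deemed, at the discretion of the Investigator, necessary to be evaluated". It requires no graded knee sign. Knee pain on the numerical rating scale does have a pre-dose value (8.1.6).

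**Population and procedure.** Inclusion criterion I6 takes a KL 2-4 target knee, "defined at screening as the knee with greater pain". Section 6.2.2 allows aspiration before the injection, in part to "free the knee from the tension linked to the excess volume of synovial fluid in the knee".

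**Analysis.** Protocol 10.1.4 counts participants with injection-site reactions, overall and by maximum severity. The SAP 12.2.5 template shows maximum grade by kind of reaction, with no baseline row. SAP 9.4 says "For any variable, the baseline value is defined as the last observation before IMP injection"; for these signs no such observation is scheduled.

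**The concern.** Tenderness, erythema and swelling at the injection site are named in the primary safety endpoint (Protocol 3.2.1), and Protocol 2.3 says there are no human data on safety after intra-articular injection. Yet the first grading of these signs comes one hour after dosing. A knee that was tender or swollen on arrival can look the same at one hour as a knee that reacted to the injection.

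Two uses of the data are exposed. The first is the descriptive comparison of any-grade local reactions between each dose group and pooled placebo. The second is the case-by-case judgement of relatedness. The stopping rule in 4.6.1 covers a severe local reaction judged related to the product, and close timing is one of its stated grounds. A sign first graded after dosing appears close in time whether or not it was there before. Optional aspiration can also change swelling just before injection, with no earlier grade to compare.

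The other primary safety measures summarised over time (knee pain, vital signs, ECG, laboratory values, glycemia) all have a pre-dose value and a change from baseline in the SAP. Local signs do not.

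**Working it through.** **Inputs from the documents.** Protocol 1.1: 32 participants in 4 cohorts, 6 active to 2 placebo. Check: 4 × (6 + 2) = 32, with 24 active and 8 placebo, so each dose group of 6 is set against a pooled placebo group of 8. The documents state no local reaction rate, effect size or power, so there is no other figure to reproduce.

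**Assumptions.**
- b is the share of knees that already show at least one sign, and all such signs are recorded as reactions. Range 10% to 60%.
- True new-reaction rates are r = 30% on active and p = 5% on placebo, for illustration only.
- New reactions are independent of signs already present.

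**Formulas.**
- Observed rate: active b + (1-b)r, placebo b + (1-b)p.
- Observed difference: (1-b)(r-p).
- Chance of at least one pre-existing sign in a group of n: 1 - (1-b)^n.
- Standard deviation of the dose-placebo difference from background alone: √[b(1-b)(1/6 + 1/8)].
- Chance that the dose group shows the higher observed proportion: exact binomial sum over all outcomes for 6 and 8 participants.

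**Results.**

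| b | Observed active / placebo | Difference | Ratio | At least one sign: of 6 / of 8 | Background SD | Chance dose group looks higher |
|---|---|---|---|---|---|---|
| 0 | 30.0% / 5.0% | 25.0 points | 6.00 | 0 / 0 | 0 | 86% |
| 10% | 37.0% / 14.5% | 22.5 | 2.55 | 47% / 57% | 16 points | 83% |
| 20% | 44.0% / 24.0% | 20.0 | 1.83 | 74% / 83% | 22 | 77% |
| 30% | 51.0% / 33.5% | 17.5 | 1.52 | 88% / 94% | 25 | 71% |
| 50% | 65.0% / 52.5% | 12.5 | 1.24 | 98% / 99.6% | 27 | 66% |
| 60% | 72.0% / 62.0% | 10.0 | 1.16 | 99.6% / 99.9% | 26 | 65% |

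Worked line, b = 30%: active 0.30 + 0.70 × 0.30 = 0.51; placebo 0.30 + 0.70 × 0.05 = 0.335; difference 0.175 = 0.70 × 0.25. Background SD = √(0.21 × 0.2917) = 0.247.

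**Reading.** The absolute difference falls in proportion to (1-b); the ratio falls much faster. The expected background is the same in both arms, so there is no systematic tilt. From b = 30% upwards, though, chance imbalance in background alone (SD about 25 points or more) is as large as the assumed true effect.

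**The case against.** **Unworsened signs should not be counted.** The primary endpoint counts adverse events. Protocol 11.3.1 excludes anticipated fluctuation of pre-existing conditions that do not worsen, and SAP 12.2.5 introduces its table as adverse event details. This stands in part. A reader might infer that signs already present *are* counted as reactions; the documents do not say so, and the most they support is that such signs *can be* counted. The rule still needs a reference grade to apply or verify it, and none is scheduled. Section 8.1.5 also records any finding on its own three-grade scale, and Protocol 10.1.4 summarises injection-site reactions separately from adverse events related to local tolerability.

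**The drug effect is not lost.** A reader might infer that any true effect is diluted. That is too strong. The (1-b) factor applies to any-grade incidence only. Maximum grade still shows a rise from mild to severe, and the stopping rule and the events of special interest concern severe reactions. Randomised, blinded placebo makes the background equal in expectation. All of this stands.

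**The size is assumed.** True: b and both rates are assumptions, and at b = 10% the shrinkage is only 10%. The case from pain and excess fluid bears on tenderness and swelling, less on erythema. Exclusions E9 and E10 remove active infection, crystal disease and inflammatory joint disease, though not osteoarthritic tenderness or effusion. No significance tests are planned, so the cost is to description and causality judgement.

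**Pre-dose information exists.** An examination and a pain score are taken at T0-4h, and the Investigator manual, which is not available here, may ask for more. But neither public document requires a graded record of these signs.

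**Conclusion.** The gap is real and inexpensive to close. No graded pre-injection assessment of tenderness, erythema or swelling is scheduled, and no local tolerability summary uses a baseline. Signs already present can therefore be recorded as reactions, and the adverse event rule on unworsened conditions cannot be checked against a grade.

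If such signs are present in a share b of knees and are recorded, the any-grade difference shrinks by the factor (1-b): by 10% at b = 10% and by 60% at b = 60%. On assumed true rates of 30% and 5%, the chance that a dose group of 6 shows a higher rate than the 8 placebo participants falls from 86% to 71% at b = 30%. These sizes rest on assumed inputs throughout. The harm is attenuation of the any-grade comparison plus chance imbalance at 6 versus 8. It is not directional bias, and it does not hide worsening to a higher grade.

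**What to change.** 1. **Protocol 1.2.2 and 8.1.5.** Add a local reaction entry at T0-4h: same signs and three-grade scale as post-dose, within the physical examination already scheduled and before any aspiration. Record whether aspiration was done.
2. **SAP 12.2.5.** Show the pre-dose grades as a baseline row. Report new or worsened signs *alongside* any post-dose sign, not instead of it. Counting a reaction only when it exceeds the pre-aspiration grade could erase real ones: if fluid is removed and swelling then returns to its earlier grade because of the injection, that event would disappear.
3. **Participants dosed before the change.** State the missing baseline as a limitation in the clinical study report, and give the new-or-worsened count only where a pre-dose grade exists, with its denominator.

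**Cost.** One more grading per participant, an eCRF field for the grades and one for aspiration, and a short SAP addition; no extra visit or blood sample. The main limit is timing. Protocol 2.3 reports blinded safety data from cohort 3 as of 17 July 2023, and SAP 5.1 describes enrolment in the past tense. A baseline may therefore be available only for later participants, or for none, in which case only the limitation statement remains. Where it exists for some only, dose groups would differ in what can be shown, which is a further reason to keep the any-sign count for everyone.
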